7.4.1.3. Skin Pain Numerical Rating Scale

The Skin Pain NRS is a daily patient-reported measure (24-hour recall) of the worst level of pain intensity from 0 (no pain) to 10 (worst imaginable pain). Participants will be asked, “Rate the pain severity from your atopic dermatitis skin changes by selecting a number that best describes your worst level of pain in the past 24 hours.”

The Skin Pain NRS score for baseline will be determined by averaging the 7 daily NRS scores before Day 1 (Day –7 to Day –1). The by-visit Skin Pain NRS score for postbaseline visits will be determined by averaging the 7 daily NRS scores before the visit day. If 4 or more daily scores are missing (out of the 7), the Skin Pain NRS score at the visit will be set to missing.

7.4.1.4. Body Surface Area

Total %BSA afflicted by AD will be estimated at each visit in the VC and LTS periods. Body surface area assessment will be approximated to the nearest 0.1% using the Palmar Method as guides, the palm plus 5 digits, with fingers tucked together and thumb tucked to the side (handprint), as 1% BSA and the thumb as 0.1% BSA.

7.4.1.5. Patient-Oriented Eczema Measure

The POEM is a 7-question quality-of-life assessment that asks how many days the participant has been bothered by various aspects of their skin condition during the past 7 days ([Charman et al 2004](#)).

Each of the 7 questions carries equal weight and is scored from 0 to 4 as follows:

- No days = 0
- 1 to 2 days = 1
- 3 to 4 days = 2
- 5 to 6 days = 3
- Every day = 4

The POEM is calculated by summing the score of each question resulting in a maximum of 28 and a minimum of 0. The meaning of POEM scores can be categorized as follows:

- 0 to 2 = Clear or almost clear
- 3 to 7 = Mild eczema
- 8 to 16 = Moderate eczema
- 17 to 24 = Severe eczema
- 25 to 28 = Very severe eczema

If 1 question is left unanswered, this is scored 0, and the scores are summed and expressed as usual out of a maximum of 28. If 2 or more questions are left unanswered, the questionnaire is not scored. If 2 or more response options are selected, the response option with the highest score should be recorded.

The total POEM score and POEM scores in each category will be summarized by visit and by treatment.

7.4.1.6. Dermatology Life Quality Index and Children's Dermatology Life Quality Index

The DLQI ([Finlay and Khan 1994](#)) is a simple 10-question validated questionnaire for use in participants aged 16 years and over to measure how much the skin problem has affected the participant over the previous 7 days.

The scoring of each question is as follows: Very much = 3; A lot = 2; A little = 1; Not at all = 0; Not relevant = 0; Question 7, “Prevented work or studying” = 3.

The following imputation will be applied for incorrectly completed questionnaires:

- If 1 question is left unanswered, this is scored 0 and the scores are summed and expressed as usual out of a maximum of 30.
- If 2 or more questions are left unanswered, the questionnaire is not scored.
- If question 7 is answered “yes,” this is scored 3. If Question 7 is answered “no,” but then either “a lot” or “a little” is ticked, this is then scored 2 or 1. If “Not relevant” is ticked, the score for Question 7 is 0. If it is answered “no,” but the second half is left incomplete, the score will remain 0.
- If 2 or more response options are ticked, the response option with the highest score should be recorded.
- If there is a response between 2 tick boxes, the lower of the 2 score options should be recorded.
- For DLQI 6 subscales, if the answer to one question in a subscale is missing, that subscale should not be scored.

The DLQI is calculated by summing the score of each question resulting in a maximum of 30 and a minimum of 0. The higher the score, the more quality of life is impaired.

The meaning of total DLQI scores can be categorized as follows:

- 0 to 1 = No effect
- 2 to 5 = Small effect
- 6 to 10 = Moderate effect
- 11 to 20 = Very large effect
- 21 to 30 = Extremely large effect

A change from baseline in DLQI and CDLQI score of at least 4 points is considered clinically important (Basra et al 2015, Waters et al 2010).

The questionnaire is also analyzed under 6 sub-scales as follows:

- Symptoms and feelings (Questions 1 and 2)
- Daily activities (Questions 3 and 4)
- Leisure (Questions 5 and 6)
- Work and school (Question 7)
- Personal relations (Questions 8 and 9)
- Treatment (Question 10)

CDLQI (Lewis-Jones and Finlay 1995) is the youth/children's version of the DLQI and will be completed by adolescents aged ≥ 12 years to < 16 years. The scoring of each question is Very much = 3; Quite a lot = 2; Only a little = 1; Not at all = 0; Question unanswered = 0; Question 7: "Prevented school" = 3. The CDLQI is calculated by summing the score of each question resulting in a maximum of 30 and a minimum of 0. The higher the score, the more quality of life is impaired.

The questionnaire is also analyzed under 6 subscales as follows:

- Symptoms and feelings (Questions 1 and 2)
- Leisure (Questions 4, 5, and 6)
- School or holidays (Question 7)
- Personal relationships (Questions 3 and 8)
- Sleep (Question 9)
- Treatment (Question 10)

The severity banding for CDLQI scores:

- 0 to 1 = No effect on child's life
- 2 to 6 = Small effect
- 7 to 12 = Moderate effect

- 13 to 18 = Very large effect
- 19 to 30 = Extremely large effect

The following imputation will be applied for incorrectly completed questionnaires for CDLQI:

1. If one question is left unanswered, this is scored 0, and the scores are summed and expressed as usual out of a maximum of 30.
2. If 2 or more questions are left unanswered, the questionnaire is not scored.
3. If both parts of Question 7 are completed, the higher of the 2 scores should be counted.

7.4.1.7. Patient Global Impression of Change

The PGIC is a participants' self-reporting measure that reflects their belief about the efficacy of treatment. The PGIC is a 7-point scale depicting a participant's rating of overall improvement and will be captured during site visits during the VC period (1, very much improved; 2, much improved; 3, minimally improved; 4, no change; 5, minimally worse; 6, much worse; 7, very much worse). Missing values will not be imputed.

A participant is said to be a PGIC responder or have achieved a PGIC response if he or she has achieved PGIC of (1) very much improved or (2) much improved.

7.4.1.8. EQ-5D-5L

The EQ-5D-5L ([EuroQol Research Foundation 2017](#)) is a validated, self-administered, generic utility questionnaire wherein participants (adolescents and adults) rate their current health state based on the following criteria (dimensions): mobility, self-care, usual activities, pain/discomfort, and anxiety/depression.

During all VC period study visits (starting at screening) and at specific LTS visits (Weeks 12, 24, 36, 52, and follow-up visit), the participant will be asked to indicate his/her health state over the past 7 days.

Missing values will not be imputed. The categorical outcomes for the 5 dimensions (mobility, self-care, usual activity, pain/discomfort, and anxiety/depression) will be summarized. The change from baseline in EQ-5D VAS score will be analyzed.

7.4.1.9. Work Productivity and Activity Impairment Questionnaire: Specific Health Problem Version 2.0

The WPAI:SHP v2.0 ([Reilly et al 1993](#)) questionnaire is a validated 6-item instrument, completed during all site visits starting at screening, during the VC period, and at specific LTS visits (Weeks 12, 24, 36, 52 and follow-up visit) that measures the effect of overall health and specific symptoms on productivity at work and regular activities outside of it during the past 7 days.

WPAI outcomes are expressed as impairment percentages, with higher numbers indicating greater impairment and less productivity, i.e., worse outcomes, as follows:

Questions:

- 1 = currently employed
- 2 = hours missed due to AD
- 3 = hours missed other reasons
- 4 = hours actually worked
- 5 = degree AD affected productivity while working
- 6 = degree AD affected regular activities

Scores:

Multiply scores by 100 to express in percentages.

- Percent work time missed due to AD: $Q2 / (Q2 + Q4) \times 100$
- Percent impairment while working due to AD: $Q5 / 10 \times 100$
- Percent overall work impairment due to AD: $[Q2 / (Q2 + Q4)] + ((1 - [Q2 / (Q2 + Q4)]) \times (Q5 / 10)) \times 100$
- Percent activity impairment due to AD: $Q6 / 10 \times 100$

These impairment percentages will be summarized by visit and by treatment. Missing values will not be imputed.

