To further evaluate efficacy of ruxolitinib cream.	
• Proportion of participants with a clinically meaningful (\geq 6-point) improvement in the PROMIS Short Form – Sleep-Related Impairment (8a) and Sleep Disturbance (8b) 24-hour recall score at Weeks 2 and 4.• Change from baseline in PROMIS Short Form – Sleep-Related Impairment (8a) 24-hour recall and Short Form – Sleep Disturbance (8b) 24-hour recall score at Weeks 2, 4, and 8.• PROMIS Short Form – Sleep-Related Impairment (8a) 7-day recall and Short Form – Sleep Disturbance (8b) 7-day recall score at Weeks 8, 12, 24, and 52.• Change from baseline in AD afflicted %BSA at every visit.
To evaluate the participants' Quality of Life and other patient-reported outcomes.	
• Change from baseline in POEM score at each visit.• Change from baseline in DLQI score at Weeks 2, 4, 8, 12, 24, and 52 and at unscheduled visits.• Mean PGIC score at Weeks 2, 4, and 8.• Proportion of participants with each score on the PGIC at Weeks 2, 4, and 8.• Proportion of participants with a score of either 1 or 2 on the PGIC at Weeks 2, 4, and 8.• Change from baseline in EQ-5D-5L score during the VC period.• Change from baseline in WPAI:SHP v2.0 at Weeks 2, 4, 8, 12, 24, 36, and 52.
To evaluate the PK of ruxolitinib cream in plasma.	
• Trough plasma concentrations of ruxolitinib at all study visits.

[figure not shown]
For an EMA submission, if applicable, the primary endpoint is changed to the proportion of participants who achieve EASI75 at Week 8, and the first key secondary endpoint is changed to the proportion of participants achieving IGA-TS at Week 8.

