7.4.2.1. Continuous Efficacy Endpoints

By-visit summary statistics for the following continuous measurements, including change from baseline and percentage change from baseline will be presented:

- EASI score
- By-visit Itch NRS score
- By-visit Skin Pain NRS score
- By-visit PROMIS Short Form – Sleep-Related Impairment (8a) 24-hour recall total raw score
- By-visit PROMIS Short Form – Sleep Disturbance (8b) 24-hour recall total raw score

The summary statistics includes sample size, mean, median, standard deviation, minimum, maximum, 1st quartile, 3rd quartile, and 95% CI will be presented by visits. An MMRM may be fit for the comparisons between ruxolitinib cream groups and vehicle cream group at Week 8. The MMRM will include the fixed effect of treatment, stratification factor, the visit, and

treatment by visit interaction. The variance-covariance matrix of the within-participant errors in MMRM will be modeled as unstructured.

For the following continuous measurements, the change from baseline to Week 8 will be analyzed using an ANCOVA model with treatment and stratification factors and baseline score as covariates if applicable.

- Total AD afflicted %BSA
- Total SCORAD score
- Total POEM score
- Total DLQI/CDLQI score
- DLQI/CDLQI subscores
- EQ VAS score
- WPAI:SHP v2.0 scores

For the above continuous measurements during the LTS period, only summary statistics will be presented.

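### The SAP's formula for WPAI overall work impairment lacks an outer bracket: only the second term is multiplied by 100, so the score is too low for anyone who missed work

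*SAP*

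**What the plan says.** SAP Section 7.4.1.9 lists the WPAI:SHP items and four derived scores. The items that matter here are "2 = hours missed due to AD", "4 = hours actually worked" and "5 = degree AD affected productivity while working". On scale and direction the section states: "WPAI outcomes are expressed as impairment percentages, with higher numbers indicating greater impairment and less productivity". Above the formulas it instructs: "Multiply scores by 100 to express in percentages".

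The overall work impairment score is then printed as "Q2 / (Q2 + Q4)] + ((1 - [Q2 / (Q2 + Q4)]) \times (Q5 / 10)) \times 100", with an opening square bracket immediately before the quoted run. No outer bracket encloses the sum.

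SAP Section 2.2 (Table 1) lists as a secondary endpoint "Change from baseline in WPAI:SHP v2.0 at Weeks 2, 4, 8, 12, 24, 36, and 52". SAP Section 7.4.2.1 includes "WPAI:SHP v2.0 scores" among the measurements whose change from baseline to Week 8 is analysed by ANCOVA. The Protocol's description of the questionnaire (Section 8.2.7.5) gives no scoring formula that could override the SAP.

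**The concern.** Under ordinary operator precedence the final factor of 100 belongs to the product in the second term alone. The first term, the share of work time missed, remains a proportion while the second term is a percentage, so the two are added on different scales. Missed work can then contribute at most 1 point directly. It also shrinks the second term, because that term is weighted by the share of time actually worked.

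A program that follows the line literally would give wrong values for every employed participant with missed hours. Subtracting baseline does not remove the error, because it depends on hours missed, which may change during treatment. The values would go into the Week 8 ANCOVA and planned Tables 2.13.1.1 and 2.13.1.2 (SAP Appendix A). Protocol Section 8.2.8 also names the WPAI as a source of health economic data. Since SAP Section 1 applies the plan to both INCB 18424-303 and INCB 18424-304, the error could reach two studies.

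**Working it through.** The documents give no numerical WPAI result, so there is no stated figure to reproduce. The check is algebra on the printed formula, followed by illustrative inputs.

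**Notation.** A = Q2/(Q2 + Q4), from 0 to 1. B = Q5/10, with Q5 assumed to be an integer from 0 to 10.

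**Printed form.** L = A + 100 × (1 − A) × B. The brackets in the printed line balance: two opening and two closing square brackets, five opening and five closing round ones.

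**Form consistent with the rest of the section.** F = 100 × [A + (1 − A) × B].

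**Difference.** F − L = 100A + 100(1 − A)B − A − 100(1 − A)B = 99A. It does not depend on Q5 and is zero only when Q2 = 0.

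**Direction.** The slope of L in A is 1 − 100B; the slope of F is 100(1 − B).

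- Q5 = 0: L has slope +1, F has +100.
- Q5 = 3: L has slope 1 − 30 = −29, F has +70.
- Q5 = 5: L has slope 1 − 50 = −49, F has +50.

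So for Q5 of 1 or more the printed score falls as missed work rises, against the stated direction. F never falls.

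**Worked values** (hours and ratings are illustrations for a 40-hour week, not trial data):

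| Q2 missed | Q4 worked | Q5 | A | B | L as printed | F bracketed | F − L = 99A |
|---|---|---|---|---|---|---|---|
| 0 | 40 | 5 | 0 | 0.5 | 0 + 50 = 50.0 | 50.0 | 0 |
| 4 | 36 | 3 | 0.10 | 0.3 | 0.10 + 27 = 27.1 | 37.0 | 9.9 |
| 10 | 30 | 5 | 0.25 | 0.5 | 0.25 + 37.5 = 37.75 | 62.5 | 24.75 |
| 20 | 20 | 8 | 0.50 | 0.8 | 0.50 + 40 = 40.5 | 90.0 | 49.5 |
| 40 | 0 | 0 | 1 | 0 | 1 + 0 = 1.0 | 100.0 | 99.0 |

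The last row needs a recorded Q5 of 0 from someone who worked no hours. If Q5 is blank in that case, Section 7.4.1.9 does not impute it and neither form yields a score.

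**Change from baseline.** Take baseline (20 h missed, 20 h worked, Q5 = 5) and Week 8 (0, 40, 3).

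- Bracketed: 75.0 to 30.0, an improvement of 45 points.
- Printed: 0.5 + 25 = 25.5 to 30.0, a worsening of 4.5 points.

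**Coherence with the separate work-time-missed score.** Overall impairment should never be below 100A, since F − 100A = 100(1 − A)B ≥ 0. On a grid of 1 to 40 hours missed in a 40-hour week and Q5 from 0 to 10 (40 × 11 = 440 cells), the printed score is below 100A in 311 cells. The bracketed score is below it in none.

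**Can the general instruction rescue the printed line?** Multiplying the printed result by a further 100 gives 25.5 × 100 = 2550 for (20, 20, 5), which is not a percentage.

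**The case against.** The strongest reply is that the intent is plain. The section calls the scores percentages, says to multiply them by 100, says higher is worse, and scales the other three scores correctly. A careful programmer would probably supply the missing bracket, so harm arises only if the line is followed literally. That is fair, and it makes this a misprint rather than a different intended endpoint. But the line is the scoring specification, and a SAP should not rely on the programmer to correct it.

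Several limits also stand:

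- Only one of four WPAI scores is affected, and missed work is still reported correctly in its own score.
- The 100-fold shrinkage concerns the additive term; the weighting by time worked in the second term is right.
- The wrong direction requires Q5 of 1 or more.
- The WPAI is outside the hierarchy in SAP Section 3.2, and long-term period results are descriptive only.
- The documents give no employment rate or distribution of missed hours, so the effect on a treatment contrast cannot be estimated. About 20% of participants are to be adolescents, and the score concerns only those employed.
- The formula was read from text converted from PDF. The brackets balance, so loss of a single bracket is unlikely, but loss of an outer pair cannot be excluded. The source page should be checked.

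None of these points makes the printed formula correct.

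**Conclusion.** The concern holds. The printed score equals A + 100(1 − A)B and conflicts with the scaling and direction stated in its own section. If programmed as printed, it is too low by 99 × Q2/(Q2 + Q4) points for every participant with missed hours: 9.9 points at 10% of work time missed, 24.75 at 25% and 49.5 at 50%. When Q5 is 1 or more it moves the wrong way with missed work, and a change from baseline can reverse sign.

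The formula for the error is exact; the worked cases rest on illustrative inputs. The consequence is confined to one derived score of a secondary endpoint. Primary and key secondary inference is untouched. It should be corrected because a stated scoring rule gives wrong values when followed.

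**What to change.** In SAP Section 7.4.1.9, replace the overall work impairment formula with:

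`100 × { Q2/(Q2 + Q4) + [1 − Q2/(Q2 + Q4)] × (Q5/10) }`

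Make the same correction in the derived-dataset specification. Check the analysis program against a few hand-worked cases with missed hours, such as (10, 30, 5) = 62.5 and (4, 36, 3) = 37.0; a case with no missed hours would not reveal the error. The cost is one pair of brackets and a short program check, with no change to design, data collection or sample size.

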7.4.2. Secondary Efficacy Analysis

All secondary efficacy analyses will be conducted based on the ITT population in the VC and LTS periods.

7.4.2.1. Continuous Efficacy Endpoints

By-visit summary statistics for the following continuous measurements, including change from baseline and percentage change from baseline will be presented:

- EASI score
- By-visit Itch NRS score
- By-visit Skin Pain NRS score
- By-visit PROMIS Short Form – Sleep-Related Impairment (8a) 24-hour recall total raw score
- By-visit PROMIS Short Form – Sleep Disturbance (8b) 24-hour recall total raw score

The summary statistics includes sample size, mean, median, standard deviation, minimum, maximum, 1st quartile, 3rd quartile, and 95% CI will be presented by visits. An MMRM may be fit for the comparisons between ruxolitinib cream groups and vehicle cream group at Week 8. The MMRM will include the fixed effect of treatment, stratification factor, the visit, and

treatment by visit interaction. The variance-covariance matrix of the within-participant errors in MMRM will be modeled as unstructured.

For the following continuous measurements, the change from baseline to Week 8 will be analyzed using an ANCOVA model with treatment and stratification factors and baseline score as covariates if applicable.

- Total AD afflicted %BSA
- Total SCORAD score
- Total POEM score
- Total DLQI/CDLQI score
- DLQI/CDLQI subscores
- EQ VAS score
- WPAI:SHP v2.0 scores

For the above continuous measurements during the LTS period, only summary statistics will be presented.

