2.2. Objectives and Endpoints

[Table 1](#) presents the objectives and endpoints.

Table 1: Objectives and Endpoints

Objectives	Endpoints
Primary	
To establish the efficacy of ruxolitinib cream in participants with AD.	
 • Proportion of participants achieving IGA-TS at Week 8.^a
Key Secondary	
To further assess the treatment effects of ruxolitinib cream.	
 • Proportion of participants who achieve EASI75 at Week 8.^a • Proportion of participants with a \geq 4-point improvement in Itch NRS score from baseline to Week 8. • Proportion of participants with a clinically meaningful (\geq 6-point) improvement in the PROMIS Short Form – Sleep Disturbance (8b – 24-hour recall) score at Week 8. • Proportion of participants with a clinically meaningful (\geq 6-point) improvement in the PROMIS Short Form – Sleep-Related Impairment (8a – 24-hour recall) score at Week 8.
Secondary	
To evaluate the safety and tolerability of ruxolitinib cream.	The frequency and severity of AEs; physical examinations; vital signs; and laboratory data for hematology, serum chemistry, and urinalysis.
To further evaluate efficacy of ruxolitinib cream.	
 • Proportion of participants achieving an IGA-TS at Weeks 2 and 4. • Proportion of participants achieving an IGA of 0 or 1 at each visit. • Proportion of participants with a \geq 4-point improvement in Itch NRS score from baseline to Weeks 2 and 4. • Proportion of participants who achieve EASI50 at each visit during the VC period. • Proportion of participants who achieve EASI75 at Weeks 2 and 4. • Proportion of participants who achieve EASI90 at each visit during the VC period. • Mean percentage change from baseline in EASI score at each visit during the VC period. • Mean percentage change from baseline in SCORAD score at each visit during the VC period. • Change from baseline in Itch NRS score at each visit during the VC period. • Time to achieve Itch NRS score improvement of at least 2, 3, or 4 points. • Change from baseline in Skin Pain NRS score at each visit during the VC period.

Table 1: Objectives and Endpoints (Continued)

Objectives	Endpoints

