7.1. General Considerations

For all continuous variables, both the actual value and change and/or percentage from baseline (if available) will be analyzed.

All by-visit analyses will include the follow-up period if the data are available.

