7.4.2.2. Daily Continuous Efficacy Endpoints

For the following daily continuous measurements, summary statistics including sample size, mean, median, standard deviation, minimum, maximum, 1st quartile, 3rd quartile, and 95% CI will be presented by day. An ANOVA model will be fit for the comparisons between ruxolitinib cream and vehicle cream at Week 8 on change and percentage from baseline. The ANOVA model will include treatment groups.

- Daily Itch NRS score
- Daily Skin Pain NRS score
- Daily PROMIS Short Form – Sleep-Related Impairment (8a) 24-hour recall total raw score
- Daily PROMIS Short Form – Sleep Disturbance (8b) 24-hour recall total raw score

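### The optional MMRM and the daily-score ANOVA omit the baseline score, which generally costs precision on absolute change; other change endpoints in the same SAP section are adjusted for it

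*SAP*

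**What the plan says.** SAP 7.4.2.1 makes the mixed model optional: "An MMRM may be fit for the comparisons between ruxolitinib cream groups and vehicle cream group at Week 8". It covers EASI and the by-visit Itch NRS, Skin Pain NRS and PROMIS 8a and 8b 24-hour scores. On its terms the SAP says "The MMRM will include the fixed effect of treatment, stratification factor, the visit, and" then closes the list with the treatment-by-visit interaction and an unstructured covariance. The response variable is not named in that sentence. SAP 7.1 leaves it open: "both the actual value and change and/or percentage from baseline (if available) will be analyzed".

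The same section handles change to Week 8 in %BSA, SCORAD, POEM, DLQI/CDLQI, EQ VAS and WPAI with an "ANCOVA model with treatment and stratification factors and baseline score as covariates if applicable".

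SAP 7.4.2.2 commits to an ANOVA on change and percentage change at Week 8 for the daily itch, pain and PROMIS scores. Its content is one line: "The ANOVA model will include treatment groups".

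SAP Table 1 lists "Change from baseline in Itch NRS score at each visit during the VC period", "Change from baseline in Skin Pain NRS score at each visit during the VC period" and, at Weeks 2, 4 and 8, "Change from baseline in PROMIS Short Form – Sleep-Related Impairment (8a) 24-hour recall" together with the 8b score. For EASI, Table 1 lists mean percentage change instead. Protocol 10.4.2 says only that a mixed model may be used and names no covariates. SAP 10.1, which lists departures from the Protocol, is silent on this.

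**The concern.** One section of the SAP adjusts one group of change endpoints for baseline and leaves another group unadjusted, without giving a reason. The baseline score is already collected, and in a change-from-baseline analysis it is usually a strong predictor of the response. Leaving it out generally means a wider interval from the same participants. The daily-score ANOVA also drops baseline IGA and region, the two randomisation factors.

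What is at stake is the precision of the by-visit change estimates for itch, skin pain and sleep, which are listed secondary endpoints, and of the supportive daily-score comparisons.

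**Working it through.** **The plan's own figure.** The only design figure in the documents is power above 95% for IGA-TS (Protocol 10.1, SAP 3.3). With 240 versus 120 participants and 2-sided alpha 0.025, exact Fisher power is 98.9% for 30% versus 10% and above 99.9% for 45% versus 10%, so that statement reproduces. It concerns the binary primary endpoint and does not depend on this point. No figure is given for the continuous endpoints.

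**Inputs.** From the documents: about 600 participants at 2:2:1, so 240 / 240 / 120, and two strata, baseline IGA and region (SAP 3.1). Assumed, because the documents give none:
- r, the within-arm correlation of baseline with Week 8: 0.3, 0.5, 0.7
- k = SD(baseline) / SD(Week 8): central value 1
- R², the share of baseline variance explained by the strata in the model: 0 or 0.2, with Week 8 related to the strata only through baseline
- an absolute-change response, with the same slope on baseline in every arm

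**Variance ratio.** With Week 8 SD set to 1, the residual variance of change is (1 − r²) with baseline in the model and (1 − r²) + (k − r)²(1 − R²) without it. The ratio, with over without, is

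(1 − r²) / [(1 − r²) + (k − r)²(1 − R²)]

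Example: k = 1, r = 0.5, R² = 0 gives 0.75 / (0.75 + 0.25) = 0.75.

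| k | R² | r = 0.3 | r = 0.5 | r = 0.7 |
|---|---|---|---|---|
| 1 | 0 | 0.65 | 0.75 | 0.85 |
| 1 | 0.2 | 0.70 | 0.79 | 0.88 |
| 0.8 | 0 | 0.78 | 0.89 | 0.98 |
| 1.25 | 0 | 0.50 | 0.57 | 0.63 |

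Interval width scales with the square root. For k = 1 and R² = 0 it is 0.81 / 0.87 / 0.92 of the unadjusted width. The ratio is 1 when k = r.

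**Unequal slopes.** Take baseline SD 1, residual SD 0.8 (variance 0.64), slope b in each arm, and arms of 120 / 240 / 240. A common-slope ANCOVA uses approximately the weighted slope b̄ = 0.2 × b(vehicle) + 0.8 × b(active). The variance of an active-versus-vehicle contrast is then
- with baseline: the sum over the two arms of [0.64 + (b − b̄)²] / n
- without baseline: the sum over the two arms of [0.64 + (b − 1)²] / n

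For slopes of 1.0 (vehicle) and 0.3 (active), b̄ = 0.44:
- with: (0.64 + 0.3136)/120 + (0.64 + 0.0196)/240 = 0.01070
- without: 0.64/120 + (0.64 + 0.49)/240 = 0.01004
- ratio 1.07

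The same formula gives 0.72 for slopes of 0.5 in all arms, 0.82 for 0.7 versus 0.3, and 0.99 for 0.9 versus 0.3. Simulations of the same settings agree, with a loss of 6% to 8% in the 1.0 versus 0.3 case. All these slopes are assumed.

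**Validity.** In 4,000 simulated null comparisons per correlation (240 versus 120, k = 1), type I error was 4.3% to 5.3% without baseline and 4.5% to 5.6% with it. Both are nominal.

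**The case against.** The strongest reply is that nothing here is invalid. The mixed model is optional, these analyses carry no alpha, and randomisation keeps the unadjusted estimates unbiased in expectation. That stands, and it sets the weight of the point. A reader might infer bias, inflated error or damage to the trial's main conclusions. The documents do not support that: the primary and key secondary endpoints are tested by logistic regression (SAP 7.2.2 and 7.3.2).

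Second, a reader might infer that both omissions affect listed endpoints. They do not. Table 1 names by-visit scores, which for itch, pain and PROMIS are 7-day averages (SAP 7.3.1 and 7.4.1.3). Single-day scores are not Table 1 change endpoints, so the ANOVA part is supportive only.

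Third, the calculation assumes an absolute-change response, which the MMRM sentence does not state. For percentage change, including the listed EASI endpoint, the gain may be nil, and none is claimed.

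Fourth, one slope for all arms cannot be taken for granted. In the Phase 2 study, EASI improved by 78.5% on 1.5% BID and by 26.9% on vehicle at Week 8 (Protocol 2.2.2.4.1). Different mean responses do not establish different slopes, but they make them plausible. The benefit is therefore likely, not guaranteed.

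Fifth, the MMRM may already carry some baseline severity through baseline IGA. That reduces the gain. However, the SAP writes of a stratification factor in the singular when there are two, so even this is not fully fixed.

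**Conclusion.** The omissions are in the text and no other section fills them. For absolute change in by-visit itch, skin pain and PROMIS 8a/8b, leaving out baseline generally loses precision. With an absolute-change response, equal SDs, a common slope and r of 0.3 / 0.5 / 0.7, adding baseline multiplies the variance by about 0.65 / 0.75 / 0.85 with no allowance for strata. The gain is smaller if the strata explain part of baseline, and it is nil at k = r. Very different slopes between arms can remove it or turn it into a small loss.

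These figures illustrate a range. It would be tempting to read them as the loss in this trial, but that loss cannot be established without an SD or a correlation. Confidence is high on what the SAP says and on the usual direction of the effect, not on its size. This is an optional improvement to secondary and supportive analyses.

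**What to change.** In SAP 7.4.2.1, state that the MMRM response is change from baseline for itch, skin pain and PROMIS 8a/8b. For these, add baseline score and baseline score-by-visit to the fixed effects, and name both stratification factors (baseline IGA and region).

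In SAP 7.4.2.2, replace the ANOVA on change with an ANCOVA on treatment, baseline score (the value from which the change is computed), baseline IGA and region. Add the two strata to the percentage-change model, which needs no baseline term on this argument.

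The cost is a few sentences and no new data. The MMRM gains three slope parameters, one each for Weeks 2, 4 and 8. With a common slope, one unneeded covariate raises the expected variance by a factor of about 1 + 1/(n − p − 2). With p = 5 that is 1 + 1/593, or 0.2%, for 600 participants, and 1 + 1/353, or 0.3%, for one active arm plus vehicle (240 + 120 = 360). The exception is the unequal-slope case in the working, where the loss can be larger.
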